6.6.1. Intra-Patient Dose-Escalation

Intra-patient dose escalation to the MTD may be considered for patients who, at the time the MTD is determined, have experienced a confirmed objective response or stable disease for at least 4 treatment cycles with SL-901; AND have not experienced any \geq Grade 3 toxicity that was considered by the Investigator to be related to SL-901; AND do not exhibit any evidence of cumulative toxicity that can be considered related to SL-901.

7. STUDY INTERVENTION DISCONTINUATION AND PATIENT DISCONTINUATION/WITHDRAWAL

7.1. Patient Withdrawal and Replacement

Patients may be withdrawn from the study for any of the following reasons:

- Patient, Investigator, or Sponsor request.
- Protocol violation.
- Non-compliance to protocol.
- AE.
- Pregnancy.
- Progression of disease that, in the opinion of the Investigator, precludes further study treatment.
- Lost to follow-up.

The reason for study withdrawal is to be documented in the patient's source documents and eCRF.

See [Section 6.4.2](#) for replacement of patients that discontinue treatment during C1. Patients that discontinue treatment after C1, for any reason and at any stage, will not be replaced.

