7.3. Treatment Discontinuation

Study drug may be discontinued for any of the following reasons:

- Progression of disease that, in the opinion of the Investigator, precludes further study treatment. After consultation with the Sponsor, SL-901 may be continued for a patient who has met the criteria for progressive disease but in the Investigator's opinion, continues to derive benefit from study treatment.
- Occurrence of an unacceptable AE, including DLT.
- Pregnancy.
- SL-901 interruption due to study drug-related toxicity for >1 cycle (i.e., >28 days). Interruptions or delays >28 days for reasons other than AEs and/or in the setting of sustained disease control may be acceptable and are to be discussed with the Medical Monitor.
- Patient requires use of a prohibited concomitant medication or therapy.
- General or specific changes in the patient's condition unacceptable for further treatment within the study parameters, in the judgment of the Investigator.
- Non-compliance.

- Lost to follow-up.
- Patient withdrawal of consent.
- Sponsor request.
- Other.

All study procedures outlined for the End-of-Treatment (EOT) visit should be performed 30 days (± 3 days) after the last study drug dose.

In Part 1a, patients who receive <75% of the planned SL-901 doses in C1 and/or discontinue from the study before completing study assessments through C2D1 for reasons other than DLT are to be replaced.

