8.7. Tumor Assessments

Tumor assessment by will occur at Screening (for identification of baseline disease) and after every 2 cycles of treatment thereafter. Response will be evaluated using Response Evaluation Criteria in Solid Tumors (RECIST) v1.1 ([Eisenhauer 2009](#)).

After completion of the EOT visit, patients will then be followed every 90 days for survival status for 12 months. The survival follow-up may be by telephone contact. If the patient discontinued study drug for reasons other than progressive disease, disease assessments should continue to be performed on an every 8-week basis (± 1 week) through 6 months after the first study drug dose and then on an every 90-day basis or until, in the judgment of the Investigator, there is evidence of relapsed or progressive disease.

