9.2. Populations for Analysis

The intent-to-treat (ITT) principle will be followed for the safety and efficacy populations. This is defined as all patients enrolled into the study and who received any amount of SL-901.

As warranted by the data, efficacy also may be assessed in a per-protocol population, defined as all patients who receive at least 1 cycle of treatment, have at least 1 post-baseline efficacy assessment, and have no major protocol violations, as defined by the Sponsor.

PK analyses will be performed on the PK population, defined as all patients who receive any amount of SL-901 and have sufficient data for PK analysis.

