9.3. Statistical Analysis Plan

9.3.1. Patient Disposition

Data tabulations will summarize the number of patients:

- Enrolled
- At least 1 SL-901 dose received
- Evaluable for safety and efficacy
- Protocol violations
- Withdrawn from study due to:
 - AE
 - Investigator request
 - Withdraw consent
 - Lost to Follow-up
 - Other reasons

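### Protocol 7.1 lets events that normally end study drug also end study participation, which conflicts with the follow-up in 8.7 and may censor OS, and by some routes PFS, informatively

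*Protocol*

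**What the plan says.** Protocol 7.1 concerns leaving the study: "Patients may be withdrawn from the study for any of the following reasons". Its list includes AE, pregnancy, protocol violation, non-compliance and "Progression of disease that, in the opinion of the Investigator, precludes further study treatment". The reason must be recorded in the source documents and the eCRF.

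Protocol 7.3 concerns leaving treatment: "Study drug may be discontinued for any of the following reasons". Its list repeats AE, pregnancy, non-compliance and, in the same words, progression.

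Protocol 8.7 sets follow-up after treatment. Survival follow-up carries no exception by reason for stopping: "After completion of the EOT visit, patients will then be followed every 90 days for survival status for 12 months". Imaging follow-up is conditional: "If the patient discontinued study drug for reasons other than progressive disease, disease assessments should continue to be performed on an every 8-week basis". The synopsis and SAP 5.2 and 12 repeat both rules.

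Protocol 9.3.5 censors PFS at the last objective progression-free observation and OS at last contact. SAP 12.1.4 takes the OS censoring date from the long-term follow-up eCRF. Protocol 9.3.1 tabulates patients under "Withdrawn from study due to", with AE as one row. SAP 11.4 takes treatment discontinuation and end of study from separate eCRF pages, each with reasons.

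**The concern.** The same clinical event can be handled as the end of drug with follow-up continuing, or as the end of the study with follow-up stopped. No text in 7.1 keeps a withdrawn patient in the 8.7 schedule, and about 25 centers are planned, so handling may well differ between sites. Study exit is also a real data path, since it has its own eCRF page and its own table rows.

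Kaplan-Meier estimates assume that censored patients have the same future risk as those still followed. A patient who leaves at progression or for toxicity plausibly has a higher risk. If follow-up ends there, the estimate is too favorable. At stake are the medians and landmark rates for PFS and OS planned in SAP 12.1.3 and 12.1.4.

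**Working it through.** **1. The two lists side by side**

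| Event | 7.1: leave study | 7.3: stop drug |
|---|---|---|
| AE | yes | yes (unacceptable AE, including DLT) |
| Progression | yes | yes, same wording |
| Pregnancy | yes | yes |
| Non-compliance | yes | yes |
| Protocol violation | yes | not listed |
| Sponsor request | yes | yes |
| Investigator request | yes | not under that name |

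**2. Which endpoint each route can affect**

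- *Objective progression.* This is itself the PFS event, and 8.7 does not continue imaging after it. Leaving then can censor OS only.
- *Progression in the Investigator's opinion without objective documentation.* The 7.1 item rests on opinion, while PFS in 9.3.5 needs objective progression. Leaving then can censor both.
- *AE or non-compliance.* 8.7 asks for continued imaging and survival contacts. Leaving the study loses both, so both endpoints can be censored.

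**3. Size for OS, progression route**

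The plan gives no event rates and has no figure to reproduce. All rates here are assumptions: median PFS 3 months, 85% of first events progression, median survival after progression 4 or 6 months, exponential times, last contact L = 0 or 1 month after progression, fraction w of progressing patients withdrawn.

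λ = ln 2/3 = 0.231 per month; progression hazard a = 0.85λ = 0.196; death without progression 0.15λ; hazard after progression μ = ln 2/4 = 0.173 or ln 2/6 = 0.116.

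True OS(t) = P0 + P1, with P0 = exp(−λt) and P1 = a[exp(−μt) − exp(−λt)]/(λ − μ).

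- 4 months: 0.0625 + 3.4 × (0.125 − 0.0625) = 0.275
- 6 months: 0.0625 + 1.7 × (0.25 − 0.0625) = 0.381

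The Kaplan-Meier curve tends to exp(−∫h), with h = (0.15λ·P0 + μR)/(P0 + R). Here R = (1 − w)P1 + w·P1(L), and P1(L) counts living patients who progressed within the last L months. Results at 12 months:

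| Survival after progression | True | w = 25%, L = 0 / 1 | w = 50%, L = 0 / 1 |
|---|---|---|---|
| 4 months | 27.5% | 30.4% / 29.7% | 35.0% / 33.0% |
| 6 months | 38.1% | 40.3% / 39.8% | 43.6% / 42.3% |

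The overstatement is 1.7 to 2.9 points at 25% and 4.2 to 7.5 points at 50%. At w = 0 it is nil.

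A simulation with other assumptions gives 1 to 2 points at 25% and 3 to 5 at 50%. It used median times to and after progression of 2/4, 3/6 and 4/8 months, death without progression at 0.02 per month, and last contact one month after progression.

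**4. Size for PFS, AE route**

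Assume λ as above, AE withdrawal at r = 0.05 or 0.10 per month, and the PFS hazard doubled afterwards. Kaplan-Meier reads exp(−6λ) = 25.0% at 6 months. The true value is exp(−6(λ + r)) + r[exp(−6(λ + r)) − exp(−12λ)]/(λ − r).

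- r = 0.05: 0.185 + 0.276 × (0.185 − 0.0625) = 21.9%, overstated by 3.1 points
- r = 0.10: 0.137 + 0.763 × (0.137 − 0.0625) = 19.4%, overstated by 5.6 points

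If the hazard is unchanged after the AE, the true value is also 25.0% and there is no bias.

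**The case against.** The best defense is that 7.1 is loosely drafted rather than an instruction to end follow-up. It says that patients may be withdrawn, it slips into treatment language, and the survival text in 8.7 is unconditional: "patients will then be followed every 90 days for survival status for 12 months". That stands as far as it goes: the text permits informative censoring and does not show that it happened. It does not remove the conflict, because a site has no rule for choosing between the routes.

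Several stronger readings are tempting, and the documents do not support them.

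- *Withdrawal at progression biases PFS.* With objective progression the event is already counted.
- *The ITT principle is breached.* Protocol 9.2 says "The intent-to-treat (ITT) principle will be followed for the safety and efficacy populations", but it then defines a population of enrolled and dosed patients. Censored patients remain in it.
- *The SAP definitions are contradicted.* SAP 12.1.3 and 12.1.4 count events regardless of withdrawal from treatment; 7.1 is about withdrawal from the study.
- *Protocol 9.3.1 builds in withdrawal for progression.* It has an AE row but none for progression.
- *The SAP ignores reasons for PFS censoring.* SAP 12.1.3 already plans to present them, and the available copy of that section may lack a censoring table, so silence there proves nothing.

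Precision also limits the practical weight. Dose cohorts have 3 to 6 patients. Even with the maximum of 60 patients in Part 1a, a 12-month OS near 38% has a half-width of about 1.96 × √(0.38 × 0.62/60) = 12 points, more than the bias at 50% withdrawn.

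**Conclusion.** The conflict between 7.1, 7.3 and 8.7 is real and can be read from the text. It opens a route to informative censoring of OS (AE, non-compliance, progression) and of PFS (AE, non-compliance, or progression without objective documentation). Whether the route was used, and how often, cannot be known from the documents.

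On the stated assumptions the overstatement is about 2 to 3 points in 12-month OS with 25% of progressing patients withdrawn, about 4 to 8 points with 50%, and about 3 to 6 points in 6-month PFS if the hazard doubles after an AE withdrawal. The OS figures cover the progression route only. Every rate behind these figures is assumed.

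The consequence is limited. PFS and OS are secondary, descriptive and single-arm, with no formal sample size. MTD, DLT and PK conclusions are unaffected. SAP 4 records that the study stopped early and that Part 1b was not started, so any effect is confined to Part 1a.

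**What to change.** - **Protocol 7.1, 7.3 and 8.7.** Reconcile them so that an event that ends study drug does not by itself end study follow-up. State that a patient who stops drug for these events continues with the EOT visit, the 8.7 assessments and the survival contacts unless consent to follow-up is withdrawn, the patient is lost, or the study closes. Add no new reason for stopping drug: protocol violation is in 7.1 but not in 7.3, and the edit should not carry it across. Say explicitly how Investigator or Sponsor request is handled.
- **Protocol 9.3.1.** Align the disposition rows with that distinction.
- **SAP 12.1.4.** Show study withdrawal by reason, from the existing End of Study eCRF, as a censoring category for OS. The section now reports only the numbers with an event and censored.
- **SAP 12.1.3.** Show study withdrawal as a distinct category within the PFS censoring reasons already planned. This also exposes progression by opinion, where 8.7 itself lets imaging stop on the Investigator's judgment.

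The cost is protocol wording and one censoring category per endpoint, with no visits beyond those that 8.7 already requires. With the study stopped, the SAP changes can still be made from reasons already collected; the protocol wording matters for any reuse of the text.

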7.2. Dose Modifications

In Part 1a, dose modifications are not allowed in the PK Run-in Period and C1.

7.3. Treatment Discontinuation

Study drug may be discontinued for any of the following reasons:

- Progression of disease that, in the opinion of the Investigator, precludes further study treatment. After consultation with the Sponsor, SL-901 may be continued for a patient who has met the criteria for progressive disease but in the Investigator's opinion, continues to derive benefit from study treatment.
- Occurrence of an unacceptable AE, including DLT.
- Pregnancy.
- SL-901 interruption due to study drug-related toxicity for >1 cycle (i.e., >28 days). Interruptions or delays >28 days for reasons other than AEs and/or in the setting of sustained disease control may be acceptable and are to be discussed with the Medical Monitor.
- Patient requires use of a prohibited concomitant medication or therapy.
- General or specific changes in the patient's condition unacceptable for further treatment within the study parameters, in the judgment of the Investigator.
- Non-compliance.

- Lost to follow-up.
- Patient withdrawal of consent.
- Sponsor request.
- Other.

All study procedures outlined for the End-of-Treatment (EOT) visit should be performed 30 days (± 3 days) after the last study drug dose.

In Part 1a, patients who receive <75% of the planned SL-901 doses in C1 and/or discontinue from the study before completing study assessments through C2D1 for reasons other than DLT are to be replaced.

7.4. Lost to Follow-Up

A patient will be considered lost to follow-up if they are unable to be contacted by the study site staff.

The following actions must be taken if a patient fails to return to the clinic for a required study visit:

- The site will attempt to contact the patient and reschedule the missed visit within 7 days of the originally planned study visit and counsel the patient on the importance of maintaining the assigned visit schedule and ascertain if the patient wishes to and/or should continue in the study.
- Before a patient is deemed lost to follow-up, the Investigator or designee will make every effort to regain contact with the patient. These contact attempts should be documented in the source documents, and at least three documented contacts are needed to consider a patient lost to follow-up.

Should the patient continue to be unreachable, he or she will be considered to have withdrawn from the study with a primary reason of lost to follow-up.

8. STUDY ASSESSMENTS

8.1. Screening Assessments

Screening assessments are performed subsequent to the patient providing an informed consent and before the first administration of SL-901 at the Run-in PK sampling day, see [Section 8.7](#). These assessments are to be performed within 28 days of the Run-in PK sampling day (during Screening), unless otherwise specified.

8.1.1. Demographic Data, Medical History, ECOG Performance Status, and Cancer History

Patient demographics, including age, sex, race, and ethnicity, are to be documented during Screening.

The medical history is to include cancer history, including the patient's primary tumor type, current disease stage, date of and disease stage at diagnosis, and all previous treatments, including systemic therapy, radiation therapy, and surgeries, as well as response to such treatment, when available.

A complete medical history is to be documented during Screening. The medical history should include a minimum of the prior 2 years, whenever possible, with information for longer durations, when feasible. ECOG performance status also is to be documented during Screening.

8.1.2. Prior Medications

All medications taken within 28 days before the initial Screening visit through the EOT visit, including nonprescription medications, dietary supplements and the specific dose/schedule of any systemic corticosteroid agents, should be recorded.

8.1.3. Contraception, Pregnancy and Pregnancy Testing

From the time of provision of written informed consent throughout the duration of the study, and for 1 month after last dose of SL-901, female subjects of childbearing potential must use a highly effective method of contraception. This also applies to any female partners of male study participants.

Serum or urine samples for beta-human chorionic gonadotropin pregnancy testing are to be collected from WOCBP during Screening to be eligible for participation in the study. A pregnancy test must be collected during the Run-in visit and this pregnancy test result must be reviewed and determined to be negative before administration of the first study drug dose at the Run-in PK sampling visit. Pregnancy testing is to be repeated monthly at the Day 1 visit of each cycle beginning with Cycle 2 and again after the last SL-901 dose, (at a time after the end of the relevant period of exposure). Pregnancy testing during the study should additionally occur at any time pregnancy is suspected.

A WOCBP is defined as any female who has experienced menarche and who has not undergone successful surgical sterilization (hysterectomy, bilateral tubal ligation, or bilateral oophorectomy) or is not postmenopausal (defined as amenorrhea ≥ 12 consecutive months; or women on hormone replacement therapy with documented serum follicle-stimulating hormone level ≥ 35 mIU/mL).

A highly effective method of contraception is defined as one that has no higher than a 1% failure rate. In this study, the only highly effective methods of contraception are:

- Combined (estrogen and progestogen containing) hormonal contraception associated with inhibition of ovulation, including oral, intravaginal, and transdermal formulations.
- Progestogen-only hormonal contraception associated with inhibition of ovulation, including oral, injectable, and implantable formulations.
- Intrauterine device.
- Intrauterine hormone-releasing system.
- Bilateral tubal occlusion.
- Vasectomized partner, provided that partner is the sole sexual partner of a study patient of child-bearing potential and that the vasectomized partner has received medical assessment of the surgical success.
- Sexual abstinence, when this is in line with the preferred and usual lifestyle of the study patient. (Periodic abstinence [.eg, calendar, ovulation, symptothermal, post ovulation methods for the female partner] and withdrawal are not acceptable methods of contraception.)

Male patients in this study must consent to use a condom throughout the duration of the study, and for 1 month after last dose of SL-901, and their female partners who are of child-bearing potential must use highly effective contraception, as listed above.

Prior to study enrollment, WOCBP must be advised of the importance of avoiding pregnancy during study participation and the potential risk factors for an unintentional pregnancy. This information will be included in the informed consent form (ICF) that must be signed by the patient. In addition, all WOCBP or fertile men with partners of childbearing potential should be instructed to contact the Investigator immediately if they suspect they or their partner might be pregnant (e.g., missed or late menstrual period) at any time during study participation.

Patients with a positive pregnancy test result during Screening are not eligible for study participation. Patients with a positive result at any time after the start of study drug administration are to have study drug permanently discontinued. Refer to [Section 8.6](#) for details regarding management of any pregnancies during the study.

8.1.4. Physical Examination

A complete physical examination, including measurement of height, is to be performed during Screening, on Day 1 of each cycle and at End of Treatment. Physical examinations are to be conducted by a physician or health professional licensed to perform physical

examinations and designated by the Investigator. The complete physical examinations should include assessment of the following:

- General appearance
- Eyes, ears, nose, and throat
- Head and neck
- Chest and lungs
- Cardiovascular system
- Gastrointestinal system (abdomen)
- Musculoskeletal system
- Lymphatic system
- Dermatologic
- Neurological (including questioning regarding whether the patient is experiencing any numbness and/or pain as well as light touch, sharp touch [skin prick], and temperature, position [proprioception], and vibration sensation testing. Additional neurological assessments are to be performed as appropriate for the patient's condition, at the Investigator's discretion.)
- Psychiatric
- Extremities

Symptom-directed (i.e., abbreviated) physical examinations are to be conducted at all other study visits.

Abnormal physical examination findings that are considered by the Investigator to be clinically significant during Screening and before initial dosing are to be reported as part of the patient's medical history. Abnormal, clinically significant examination findings following initiation of dosing are to be reported as AEs, if the finding represents worsening from baseline or new onset.

8.2. Adverse Events and Serious Adverse Events

8.2.1. Definitions

Adverse Event (AE)

An AE is any untoward medical occurrence in a study patient who is administered a medicinal product (study drug), regardless whether or not considered drug-related. An AE can therefore be any unfavorable and unintended sign including abnormal laboratory/examination findings, symptoms, or disease(s) temporally associated with the use of study drug, whether or not related to study drug. An AE can arise from any use of the drug (e.g., off-label use, use in combination with another drug) and from any route of administration, formulation, or dose, including an overdose.

Serious Adverse Event (SAE)

An AE is considered serious (i.e., an SAE) if, in the view of either the Investigator or Sponsor, it meets any of the following criteria:

- Results in death.
- Is life-threatening. Life-threatening means that the patient was at immediate risk of death from the reaction as it occurred (i.e., it does not include a reaction which hypothetically might have caused death had it occurred in a more severe form).
- Requires in-patient hospitalization or prolongation of existing hospitalization. Hospitalization admissions and/or surgical operations scheduled to occur during the study period, but planned before study entry are not considered adverse events if the illness or disease existed before the patient was enrolled in the study, provided that it did not deteriorate in an unexpected manner during the study (e.g., surgery performed earlier than planned).
- Results in persistent or significant disability/incapacity or substantial disruption of the ability to conduct normal life functions.
- Results in a congenital anomaly/birth defect.

Important Medical Event (IME)

An important medical event (IME) that may not result in death, be life-threatening, or require hospitalization may be considered serious when, based upon appropriate medical judgment, it may jeopardize the patient or subject and may require medical or surgical intervention to prevent one of the outcomes listed in the definitions for SAEs.

Note: The onset date of an SAE is defined as the date on which the event initially met serious criteria (e.g., the date of admission to a hospital). The end date is the date on which the event no longer met serious criteria (e.g., the date the patient was discharged from a hospital).

